5.2 Inclusion Criteria

There is no difference in criteria for screening and enrollment. Patients with general eyelid pathology, ptosis, corneal pathology, astigmatism, cataract, vitreous pathology, vitreous detachment, vitreous hemorrhage, retinal pathology, retinopathy of prematurity, retinal detachment, retinal tear, retinal hemorrhage, retinoblastoma, other intraocular tumors overlying or outside of the central visual axis, retinal pigmented epithelial cell pathology, choroidal pathology, optic nerve pathology, retinal artery or vein pathology may be included.

5.3 Exclusion Criteria

Patients who have a history of disease, treatments and/or surgical procedures affecting the ability for normal pupillary reaction are excluded.

5.4 Vulnerable Subjects

Subjects 3 years old and under will be recruited because this study is evaluating a routine examination in this population. This study has no more than minimal risk to the patient.

5.5 Recruitment

Subjects will be recruited through clinical practice at Children's National Health System and its Fairfax outpatient site. Subjects will be identified by the PI, [name], Vice-Chair, Department of Ophthalmology, in a review of medical records after a HIPAA authorization waiver for recruitment is granted. Subjects will be approached at a clinical care visit or an IRB approved study information letter will be sent to the participant's legally authorized representative (LAR). If the LAR expresses interest in the study, a copy of the IRB approved consent will be provided to the LAR. The informed consent will be signed by the LAR and assent will be obtained from the patient at an in-person visit before any research procedures or interventions are done.

The privacy of patients received for screening will be protected by password file encryption on Children's National Health System computers/hardware and will be viewable only to the PI, treating physicians and study staff. All study data that have been de-identified and requiring transport will be done in an encrypted flash memory drive.

5.6 Retention

There are no procedures in place to ensure retention as this study will be completed in one outpatient clinic visit for each subject.

5.7 End of Participation Criteria and Procedures

Participants are free to withdraw from participation in the study at any time upon request. An investigator may terminate subject study participation if:

- Any adverse event (AE), laboratory abnormality, or other medical condition or situation occurs such that continued participation in the study would not be in the best interest of the participant.*

- *The participant meets an exclusion criterion (either newly developed or not previously recognized) that precludes further study participation.*

This study may be temporarily suspended or prematurely terminated if there is sufficient reasonable cause. Written notification, documenting the reason for study suspension or termination will be provided by the suspending or terminating party to participants, site investigators, the funding agency and regulatory authorities (e.g. OHRP). If the study is prematurely terminated or suspended, the PI will promptly inform the IRB and will provide the reason(s) for the termination or suspension.

Circumstances that may warrant study termination or suspension include, but are not limited to:

- *Determination of unexpected, significant, or unacceptable risk to participants*
- *Insufficient study team or site participant compliance to protocol requirements*
- *Data that are not sufficiently complete and/or evaluable*
- *Determination of futility*

The study may resume once any concerns about safety, protocol compliance, data quality or funding are addressed and satisfy the sponsor, IRB and OHRP.

Section 6: Study Procedures

6.1 Informed Consent/Assent and HIPAA Authorization

Informed consent is a process that is initiated prior to the individual's agreeing to participate in the study. It continues throughout the individual's study participation. Consent and assent forms will be IRB-approved. The participant/LAR will be asked to read and review the consent document(s). Extensive discussion of risks and possible benefits of participation will be provided to the participants and their families/LAR in a language they understand. An IRB approved short form consent and a translator will be used when consenting participants who do not speak English. Illiterate subjects will have the consent form read to them aloud. Participant/parental consent will then be documented by having participants make their "mark" on the consent document in the presence of a non-study team member witness to avoid any possible coercion. The investigator will explain the research study to the participant/LAR/parent and answer any questions that may arise. All participants/parents will receive a verbal lay explanation of the purposes, procedures, and potential risks of the study and of their rights as research participants. Participants/LARs/parents will have the opportunity to carefully

review the written consent form and to ask questions prior to signing. Consent of at least one parent/LAR will be documented on the consent form (or as determined by the IRB). Assent for subjects aged 0 – 3 years old will be obtained and documented on the parental/LAR consent form.

Participants/parents will be given the opportunity to discuss the study with their surrogates and other care providers prior to agreeing to participate. The participant/parent and/or LAR will sign the informed consent document(s) prior to any procedures being done specifically for the study. The participants/LAR may withdraw consent at any time throughout the course of the trial. A copy of the informed consent document(s) will be given to the participant/LAR/parent for their records. The rights and welfare of the participants will be protected by emphasizing that the quality of their medical care will not be adversely affected if they decline to participate in this study.

6.2 Screening Process

Screening Visit Day -30 to the day of the first in-person outpatient clinic visit

- *Informed consent discussion*
- *Eligibility confirmation*
- *Medical history (diagnoses and medications)*
- *Demographics (date of birth)*

6.3 Study Interventions and Follow-Up

Patients will undergo a routine red reflex examination using a direct ophthalmoscope in a lighted and darkened exam room before and after pharmacologic dilation.

The study will only take place over one outpatient clinic visit, and there will be no follow-up other than continued medical care.

6.4 Description of Study Procedures/Evaluations

- *Medical history—ocular history from prenatal care and on will be obtained through the medical record or in person.*
- *Medication history—Current medications taken required.*
- *Physical examinations—Subject's red reflex and pupillary size will be examined using a direct ophthalmoscope in bright and dim room lighting conditions as well as before and after pharmacologic dilation. Automated vision screening using the Spot photoscreener will be performed before and after dilation.*
- *The results of the red reflex exam will be discussed with the patient during the clinic visit.*
- *Photographs of the subject's red reflex may be taken and edited to ensure anonymity. These photographs will allow for digital analysis of the patients red reflex. These photographs will be kept on password*

protected computers at Children's National Health System and on password protected encrypted flash drives. These photographs may be used for dissemination of study results such as in conference abstracts and medical journals. Once the study is complete, original photographs may be destroyed.

6.5 Study Team Training and Intervention Reliability

The study PI will be present and ensure the blinded examiner perform the red reflex test according to the current guideline recommendations.

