2.1 Background Information and Relevant Literature

The early detection of ophthalmic pathology is critical for the prevention of vision loss and systemic morbidity in rare cases. The American Academy of Pediatrics (AAP), the American Association for Pediatric Ophthalmology and Strabismus (AAPOS), the American Academy of Ophthalmology (AAO), and the American Association of Certified Orthoptists (AACO) continue to advocate for inclusion of the red reflex test (RRT) as part of the ophthalmologic screening exam in the general pediatrics clinic. However, studies to date have demonstrated that there are potential limitations to the RRT, especially in its ability to accurately and reliably detect posterior segment pathology.

Standard procedure for the RRT currently involves viewing both eyes at arms length in lighted room followed by a darkened room to assess for symmetry of the reflection in terms of brightness and color. If an abnormality is suspected, then the operator may move closer for further inspection. With its current application, the RRT introduces subjectivity in interpretation and likely variation in pupillary reflection based on factors such as, the specific lighting condition, degree of physiologic dilation, and patient movement. Differences in operator experience with the RRT may further compound the shortcomings of this exam technique. These factors unfortunately reduce the accuracy and reliability of the RRT as a screening measure.

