5.1 Study Population, Recruitment and Retention

Pediatric patients will be recruited through clinical practice at the designated study sites. Participants with known anterior segment or posterior segment pathology will be eligible for inclusion. Patients who have a history of disease, treatments and/or surgical procedures affecting the ability for normal pupillary reaction are excluded. An equal number of age matched participants with a normal anterior and posterior segment exam will be recruited from routine outpatient clinic visits. Informed consent will be obtained and will include an option to be considered for medical photography. Participants may opt out of photography and still be included in the study. For Spanish speaking participants, a telephone interpreter will be used for study recruitment and informed consent. A Spanish informed consent (developed by a Spanish medical translator from our English written consent) will be provided. Current estimated number of subjects required for the study is 200 total including 100 controls. Patient charts will be accessed from date of birth to patient's current age using either Cerner or Epic depending on the study site location. Examiners will include ophthalmology residents with one completed year of ophthalmology training. They will be blinded to participants' ophthalmologic history.

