8.6 Measures to Minimize Bias

Blinding

Examiners performing the red reflex test will be blinded to all subjects and results until all study data have been collected.

Breaking the Study Blind

Breaking the study blind for red reflex performers will be at the conclusion of the study data collection period. Intentional and unintentional breaking of the blind should be reported to the PI.

Section 9: Data Quality and Oversight

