9.1 Study Team Quality Assurance and Quality Control

Study data will be historical in nature, and therefore will be accurate to the patient's current diagnosis. All further evaluation will be reported by the red reflex examiner and this original data will be used in the analysis. Protocol deviations will be reported immediately or witnessed in person by the PI/co-investigator/study coordinator. Documents to be reviewed include clinic notes. The PI/co-investigator/study coordinator are responsible for reviewing the data each time the red reflex test is performed. The PI/co-investigator/study coordinator is responsible for addressing data quality issues.

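### The PI selects subjects from their records and then attends the blinded, subjective RRT, with no rule that keeps the reading free of unintentional cues

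*Combined protocol and SAP*

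**What the plan says.** All references are to the combined protocol and SAP.

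- **Selection.** Section 5.5: "Subjects will be identified by the PI", and this is done "in a review of medical records after a HIPAA authorization waiver for recruitment is granted".
- **Attendance.** Section 6.5: "The study PI will be present and ensure the blinded examiner perform the red reflex test", with adherence to the guidelines as the stated purpose.
- **Who is blinded.** Section 5.1 says of the resident examiners: "They will be blinded to participants' ophthalmologic history". Section 8.6 adds: "Examiners performing the red reflex test will be blinded to all subjects and results until all study data have been collected". No section blinds the PI.
- **If the blind is broken.** Section 8.6 asks for intentional and unintentional breaks to be reported, and names the PI as recipient.
- **Nature of the test.** Section 2.1 accepts that "the RRT introduces subjectivity in interpretation". It also lets the operator go in for a closer look when something seems abnormal.
- **Data review.** Section 9.1: "The PI/co-investigator/study coordinator are responsible for reviewing the data each time the red reflex test is performed". The same section lists clinic notes among the documents reviewed.

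**The concern.** The design takes children with known pathology and children with normal exams, and asks a resident to call each one without knowing which is which. The resident's ignorance of the child's status is what makes the sensitivity and specificity interpretable. The plan places beside that resident, who may have only one completed year of ophthalmology training, a senior person who has had access to the child's record. A pause, a request to repeat the view, or more time spent on some children could convey status without anyone intending it.

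Cues toward true status would raise both sensitivity and specificity, the two primary outcomes. The secondary comparison is exposed as well. Each child is read before and after dilation, and nothing keeps the PI's reaction, or the Section 9.1 review, out of the interval between the two readings. No analysis could remove the effect afterwards, because nothing in the plan would record it.

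**Working it through.** **1. Is the route in the text?** Section 5.5 and Section 6.5 both name the PI, so the overlap of roles is written into the plan. The PI's prior knowledge is clearest for cases. Controls come from routine clinic visits (5.1), although 5.5 speaks of subjects in general. Sections 5.1 and 8.6 blind the examiner only. I found no rule that limits communication during the test or requires the reading to be fixed before any exchange. Photography is optional (5.1), and no masked re-reading of photographs is described, so it is not a backstop.

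**2. The plan's own figures.** The totals of 59 and 280 in Section 8.5 reproduce with exact (Clopper-Pearson) 95% intervals of total width at most 0.20: 44/0.75 = 58.7, rounded up to 59, and 70/0.25 = 280. They do not bear on blinding. I use only the planning values behind them, 90% sensitivity and 80% specificity.

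**3. Illustrative size.** Assume that cues correct a fraction c of would-be wrong readings. Then observed = true + c × (1 − true). The documents give no c, so the values below are assumptions.

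| True value and source | c = 5% | c = 10% | c = 20% |
|---|---|---|---|
| Sensitivity 4.1% (newborn screening study, 2.1) | 8.9% | 13.7% | 23.3% |
| Sensitivity 90% (8.5) | 90.5% | 91% | 92% |
| Specificity 80% (8.5) | 81% | 82% | 84% |

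For example, 0.041 + 0.05 × 0.959 = 0.089.

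**4. Direction.** The Protocol Summary expects the RRT to be sufficient for anterior disease and insufficient for posterior disease. Upward bias therefore helps the anterior statement and works against the posterior one. Section 2.2 words the hypothesis differently and expects poor performance for both segments. Under that wording the bias works against both.

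**5. Dilation comparison.** Let s1 and s2 be the true sensitivities before and after dilation.
- Same c at both readings: the observed difference is (1 − c)(s2 − s1). Equal cueing shrinks a real difference and creates none.
- Cueing at the second reading only, with s1 = s2 = s: the spurious difference is c(1 − s). At s = 4.1% this is 4.8 points for c = 5% and 9.6 points for c = 10%. At s = 90% it is 0.5 and 1.0 points.
- In counts, take the 100 non-controls of Section 5.1, assume half are posterior cases, and assume one reading per child. About 50 × 0.959 = 48 are missed undilated. Cueing 5% to 10% of these at the second reading adds 2.4 to 4.8 one-way discordant pairs. Six such pairs with none opposing give an exact McNemar p of 2 × 0.5^6 = 0.031; five give 0.0625. Reaching six would need c of about 6/47.95 = 12.5%.

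**The case against.** The strongest reply is that the PI's presence is deliberate and useful. Section 6.5 gives its purpose as adherence to guideline technique, and Section 2.1 names differences in operator experience as a weakness of the RRT. There are also partial safeguards. Breaks of the blind must be reported, disclosing a diagnosis to the examiner would already breach 8.6, and 9.1 says the examiner's own original data are what is analysed. All of this stands, and supervision of technique should be kept. But these safeguards act on disclosure or after a break. They do not prevent an unconscious cue from shaping the original reading, and reports of a break go to the person who may be its source.

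A reader might infer four stronger things that the documents do not support.

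- **That cueing will occur, or that the blind is already lost.** The text shows an open route and nothing more.
- **That a few prompted readings would overturn the posterior conclusion.** At the assumed 5% to 10%, 4.1% becomes 8.9% to 13.7%. With 50 assumed posterior cases, 7/50 has an exact 95% interval of about 6% to 27%. That is still poor, and the plan sets no threshold of sufficiency to cross. Because cues toward the truth work against the posterior hypothesis, a poor posterior result would be conservative in this respect.
- **That posterior sensitivity is expected to be near zero here.** The 4.1% and 0% in Section 2.1 come from newborns. This study enrols children under 17 with known pathology, examined by ophthalmology residents, and states no separate posterior planning value. The illustration shrinks as true sensitivity rises.
- **That a co-investigator or coordinator could simply replace the PI.** Section 9.1 gives those roles the data review and lists clinic notes among its documents, so they may be just as unmasked.

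**Conclusion.** The point holds as a gap in procedure that is cheap to close. The plan lets a person with access to the child's record stand beside a blinded reader of a subjective test, and has no rule that protects the reading from unintentional cues. The size is unknown.

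Under the assumed 5% to 10%, the shift is 0.5 to 1 point at the planning sensitivity and 1 to 2 points at the planning specificity, small against the planned ±10%. It is 4.8 to 9.6 points if true sensitivity is as low as 4.1%, and that would not turn a poor posterior result into a good one. The more delicate result is the before-and-after dilation comparison, and only if cues differ between the two readings. These figures rest on an assumed cueing rate and, for the counts, on an even split of cases with one reading per child.

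**What to change.** Amend Section 6.5, with a matching line in Sections 8.6 and 9.1:

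- The examiner writes down and hands over each reading (lights on and lights off, before and after dilation) before any exchange with the PI.
- The PI may correct technique only, in the same way for every child, and makes no comment on findings or diagnosis until the last post-dilation reading is recorded. The existing rule in 8.6, which keeps examiners blinded until data collection ends, continues to apply after that.
- The Section 9.1 data review for that child also waits until the last reading is recorded.
- A substitute observer may be used only if confirmed unaware of that child's diagnosis and group.

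The main option needs no extra staff and keeps the PI's check on technique. The cost is a few lines of protocol text and slightly less live teaching and feedback during the visit. It has to be in place before readings are taken, since it cannot be repaired at analysis.

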6.6 Concomitant Interventions and Procedures

There are no concomitant interventions or procedures in this study. Any additional studies as part of the patient's care which may interfere with the red reflex test will be performed after the red reflex test.

Section 7: Safety Assessments and Reporting

The intervention in this study is less than minimal risk. The highest level of patient safety will be ensured as part of routine clinical care.

7.1 Adverse Events (AEs)

There are no AEs anticipated in this study.

7.2 Serious Adverse Events (SAEs)

There are no SAEs anticipated in this study.

7.3 Unanticipated Problems (UPs)

OHRP considers unanticipated problems involving risks to participants or others to include any incident, experience, or outcome that meets all of the following criteria:

- Unexpected in terms of nature, severity, or frequency given the research procedures described in the study documents (e.g., consent, protocol) the participant population; AND*
- Related or possibly related to participation in the research. "Possibly related" means there is a reasonable possibility that the incident, experience, or outcome may have been caused by the procedures involved in the research; AND*
- Suggests that the research places participants or others at a greater risk of harm (including physical, psychological, economic or social harm) than was previously known or recognized.*

At each study visit, the study team will ask the participant/LAR if any AE/SAE/UPs have occurred since the last study contact. All adverse events will be captured on the adverse events CRF. Information collected includes event term, onset date, severity, relationship to study intervention (assessed and documented by an authorized study team member), and date of event

resolution/stabilization. All events occurring while on study must be documented, regardless of relationship to the research intervention(s). All events which meet the definition of a serious adverse event or unanticipated problem that occur during the study visit will be followed until resolved or stable.

Any medical condition that is present before the first study intervention will be considered a baseline condition; it will not be reported as an AE.

Serious Adverse Event and Unexpected Problem Reporting

All suspected adverse reactions to study interventions (including comparators) that are both serious AND unexpected should be reported to the IRB. The reporting time frames are as follows:

- *Report the death of a Children's National subject enrolled in an interventional study if the death is unexpected (not due to disease progression) and related or possibly related to the research within one (1) business day of learning of the event. A follow-up report must be submitted within two (2) business days.*
- *Report all other unanticipated problems to the IRB within seven (7) days.*

If any needed information is missing or unknown at the time of initial reporting, the study team will actively try to obtain it. The study team will maintain records of efforts to obtain additional follow-up information. Any additional relevant information to a previously submitted report will be submitted to oversight bodies as soon as the information is available.

All SAEs and UPs will be followed until satisfactory resolution or until the site investigator deems the event to be chronic or stable. Other supporting documentation of the event may be requested by oversight bodies and should be provided as soon as possible.

Section 8: Statistical Considerations and Analysis

